3.1 Overall Design

Clinicians who see patients at the Center on Aging (COA) will be made aware of the study via individual meetings with co-investigators. These meetings will be by phone, Zoom, or in-person if/when feasible. Patients and caregivers will be identified through referrals from physicians practicing at the Center on Aging. They will be sent a recruitment letter in the mail one month prior to a co-investigator calling them to go over the screening and consent forms. Any study data collected for potential participants that do not meet eligibility will be immediately deleted. Informed Consent and HIPAA authorization for caregivers and patients, and informed consent for clinicians will occur orally over the phone or in-person at the COA just prior to in-person health visits when feasible as outlined in the Informed Consent section.

Patient-caregiver dyads will be randomized into either the CHEC (n=60; 30 caregivers and 30 patients) or control (usual care) condition (n=60; 30 caregivers and 30 patients). Randomization will occur through block randomization with alternative block sizes of 4 and 6 for each participating clinician.

Intervention Condition. Participants in the intervention condition will complete the Caregiver Checklist portion of CHEC at the beginning of their health visit. The participating clinician will then respond to the checklist following the guidelines on the accompanying Tip Sheet.

Control Condition. Caregivers in the control condition will receive their usual care from the participating clinician during the health visit.

Baseline (pre-visit). Caregivers in both conditions will be asked to complete identical pre-visit surveys. The survey will be scheduled to be completed over the phone, digitally on REDCap, or in-person depending on the participant's preference and COVID-19-related guidelines. We will ask about the participant's background, caregiving role, communication with providers, and feelings of caregiver preparedness. It will take approximately 20 minutes to complete. Medical chart abstraction will be used to collect patient's background characteristics, medications, diseases, and health events (e.g., hospitalization). Clinicians will complete a pre-intervention survey over the phone or in-person depending on the participant's preference and COVID-19-related guidelines. We will ask for the clinicians' personal characteristics and preparedness to assess and address caregivers' needs and concerns.

Visit. All participants will have their medical visit audio recorded.

Post-visit. All caregiver participants will complete a post-visit survey within 1 week of the visit. They will also complete follow-up surveys 2 months and 6 months after the visit.

Post-intervention. At the completion of the entire intervention period, clinicians will complete a post-intervention survey and interview. The clinician surveys and interview will take no more than 30 minutes total and will be conducted within 1 month of the conclusion of the intervention period.

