Study Description:	The goal of this project is to pilot test CHEC (Collaborative Healthcare Encounters with Caregivers) in primary care. CHEC is brief intervention with two components: 1) a checklist to identify the needs and concerns of unpaid/family caregivers who accompany older patients (aged 65+) to their primary care visits and 2) accompanying Tip Sheet for clinicians.
Sample Size:	
N = 60 caregivers*
 
N = 60 patients*
 
N = 10 primary care clinicians
 
*Participants will be a part of a patient-caregiver dyad and will be recruited together.

Enrollment:	This study will enroll 60 patient-caregiver dyads and 10 primary care clinicians. It will screen up to 200 patients, up to 200 caregivers, and up to 15 clinicians.
Study Population:	Patient participants will include individuals who have upcoming appointments at the Center on Aging (COA) and are identified by COA clinicians as typically attending appointments with a family caregiver. Patient participants will vary in age, gender, race/ethnicity, and health conditions. Family caregiver participants will include caregivers of patients receiving care at the COA. They will also vary in age, gender, and race/ethnicity. The clinician sample will include individuals who provide care at the COA. Clinicians will vary in age, be enrolled regardless of gender, and include those who have patient visits scheduled for June 2021 – August 2022.
Enrollment Period:	14 months
Study Design:	Two group single-blind randomized pilot RCT collecting: 1) survey data, 2) audio-recordings, and 3) electronic medical record data.
Description of Sites/ Facilities Enrolling Participants:	Participants will be recruited and enrolled at WCM/NYP offices, specifically the Center on Aging.
Study Duration:	August 31, 2024
Participant Duration:	Providers – 14 months Caregivers – 6 months Patients – 1 month
Primary Objective:	To examine the feasibility and acceptability of implementing CHEC in primary care practice.

Secondary Objectives:	To examine the preliminary impact of CHEC on primary care visit communication (discussion of family caregivers' needs).
Exploratory Objectives:	Not applicable

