1.1.2 Hypotheses / Research Questions

Hypothesis 1: Greater than 70% of caregivers will perceive the checklist to be an acceptable length and easy to use.

Hypothesis 2: Greater than 70% of caregivers will report that the checklist is helpful in identifying their unmet needs and starting a discussion with providers.

Hypothesis 3: Greater than 70% of caregivers and providers will report that they desire to continue using the checklist in the future.

Hypothesis 4: The checklist will not significantly impact primary care workflow or visit duration.

Hypothesis 5: Discussion of caregivers' needs and concerns will occur more often in the intervention group than in the usual care group.

Hypothesis 6: Caregiver perceptions of visit communication will be more positive in the intervention group than in the usual care group.

2. Background and Significance

In the United States, nearly 8 million older adults rely on family and other unpaid caregivers (neighbors; friends) for assistance with their health care. These caregivers collectively provide 75-80% of the total care hours to community-dwelling older adults and fill multiple roles in the health care system: attending doctor's visits, coordinating care, and assisting with treatment regimens. The availability and adequacy of assistance provided by family and unpaid caregivers have direct implications for health care costs and quality of care of older adults. Yet, caregivers are not systematically identified in care delivery systems, and their abilities and needs are not routinely assessed. Caregivers receive inadequate preparation for the tasks they must assume. They report high levels of stress and are at risk for physical illness, depression and anxiety, and sleep disturbance. If these impairments and unmet needs are not assessed and addressed, they can impede the caregiver's ability to provide effective assistance to the older adult, ultimately leading to costly hospitalizations and nursing home placements. These caregiver factors (health impairments; unmet needs) are particularly influential in the context of dementia where patients require substantial caregiving assistance.

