7.2.5 Record Retention

Essential documents are those documents that individually and collectively permit evaluation of the study and quality of the data produced. After completion of the study, all documents and data relating to the study will be kept in an orderly manner by the Investigator in a secure study file. Essential documents should be retained for 2 years after the final marketing approval in an ICH region or for at least 2 years since the discontinuation of clinical development of the IP. In addition, all subject medical records and other source documentation will be kept for the maximum time permitted by the hospital, institution, or medical practice.

8. Statistical Considerations

Feasibility and acceptability will be examined by conducting frequency and descriptive statistics (i.e. mean, median, standard deviation, range) for enrollment rates and Likert-scale items assessing satisfaction with CHEC and perceived helpfulness.

Effectiveness will be measured by the number of completed checklists that result in a conversation with providers about caregiver needs and the receipt of relevant support. The effect of CHEC on the primary outcome variable, discussion of caregivers' needs, will be examined in a general linear mixed model with intervention group and time (pre-posttest) as fixed classification

factors, and individuals as levels of a random classification factor. The model will account for pre-intervention measures and will include a group x time interaction. Additional covariates (e.g., caregiver and care recipient age) and fixed classification factors (e.g., caregiver gender, race) will also be examined. Prior to model fitting, the distribution of all study variables will be assessed.

9. Adverse Event Reporting Requirements

Adverse event (AE) monitoring and reporting is a routine part of clinical research. Safety is monitored by evaluation of adverse events reported by subjects or observed by investigators or research staff, as well as by other investigations such as clinical laboratory tests, x-rays, electrocardiographs, etc.

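### Randomisation is blocked within clinician, but Section 8 does not prespecify clinician in the between-arm analysis of discussion of caregivers' needs (H5)

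*Combined protocol and SAP*

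**What the plan says.** Section 3.1 sets the allocation: "Randomization will occur through block randomization with alternative block sizes of 4 and 6 for each participating clinician". Dyads are split 30 and 30, and control dyads get usual care from the same participating clinicians, so clinician is a stratum crossed with arm. On size, the synopsis states: "This study will enroll 60 patient-caregiver dyads and 10 primary care clinicians".

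The hypothesis at issue is in Section 1.1.2: "Hypothesis 5: Discussion of caregivers' needs and concerns will occur more often in the intervention group than in the usual care group". Section 8 gives its analysis: "The effect of CHEC on the primary outcome variable, discussion of caregivers' needs, will be examined in a general linear mixed model". The fixed terms are group and time (pre and post), and the only random term is the individual: "factors, and individuals as levels of a random classification factor". It continues: "The model will account for pre-intervention measures and will include a group x time interaction". The covariate list is open: "Additional covariates (e.g., caregiver and care recipient age) and fixed classification factors (e.g., caregiver gender, race) will also be examined". Clinician does not appear as a fixed effect, a random effect or a named covariate.

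On measurement, Section 3.1 says: "All participants will have their medical visit audio recorded". Table 1 in Section 6.1 schedules that recording at Visit 1 and nowhere else. The pre-visit caregiver survey covers communication with providers, but its items are not in the documents.

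**The concern.** Blocking within clinician removes most of the between-clinician variation from the arm difference. The analysis gets that benefit only if it also removes the variation from the error term. If discussion is observed once, at the recorded visit, the pre-post structure in Section 8 has nothing to work on and the comparison becomes a two-group test on post-visit values. Differences in level between clinicians then stay in the residual variance although they hardly affect the true sampling variance of the arm difference. The standard error is too large, the interval too wide and the test conservative.

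H5 is the only between-arm comparison with a stated model, and its estimate and interval are a main product of the pilot's impact aim. The stake is precision. Differences in clinician level do not inflate false positives here.

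**Working it through.** **No plan figure to reproduce.** The documents state no alpha, power, effect size, SD, event rate or ICC. The counts agree (30 + 30 = 60 dyads), and 60 / 10 = 6 dyads per clinician on average.

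**Formula, exact 3:3 split in each of 10 clinicians, total variance 1.**
- True variance of the arm difference: (1 − ICC) × 2/30, because clinician effects cancel.
- Expected pooled within-arm variance without clinician: each arm has 3 dyads for each of 10 clinicians, so clinician effects contribute 3 × 9 × ICC = 27 ICC to its sum of squares. Over two arms that is 54 ICC on 58 df, giving (1 − ICC) + ICC × 54/58.
- Ratio of model SE to true SE: sqrt[((1 − ICC) + ICC × 54/58) / (1 − ICC)].
- ICC 0.05: sqrt(0.9966/0.95) = 1.02. ICC 0.10: sqrt(0.9931/0.90) = 1.05. ICC 0.20: sqrt(0.9862/0.80) = 1.11. ICC 0.30: sqrt(0.9793/0.70) = 1.18.

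These are upper bounds, because incomplete blocks leave some imbalance within clinician.

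**Simulation, continuous post-only outcome.** 10 clinicians × 6 dyads, blocks alternating 4 and 6, two-sided 5% test, 10,000 trials per scenario (2,500 for d = 0.5). The comparison is an unadjusted t-test (58 df) against clinician fixed effects (49 df). The effect d = 0.74 is illustrative; it gives about 81% power with 30 per arm.

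| Assumed ICC | 0 | 0.05 | 0.10 | 0.20 | 0.30 |
|---|---|---|---|---|---|
| SE ratio, no clinician | 1.00 | 1.01 | 1.04 | 1.10 | 1.15 |
| Type I error, no clinician | 0.048 | 0.046 | 0.041 | 0.030 | 0.025 |
| Power d = 0.74, without | 0.81 | 0.82 | 0.82 | 0.83 | 0.84 |
| Power d = 0.74, with strata | 0.80 | 0.82 | 0.84 | 0.87 | 0.91 |
| Power d = 0.5, without | 0.47 | 0.47 | 0.48 | 0.47 | 0.49 |
| Power d = 0.5, with strata | 0.46 | 0.48 | 0.50 | 0.55 | 0.61 |

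With strata, type I error is 0.046–0.052. The 95% half-width falls from 0.51 to 0.50 SD at ICC 0.10 and from 0.51 to 0.44 SD at ICC 0.30. With unequal volumes (14, 10, 8, 7, 6, 5, 4, 3, 2, 1) the SE ratios are 0.99 / 1.02 / 1.03 / 1.08 / 1.13. A separate simulation of 6,000 trials per scenario gave 1.00 / 1.02 / 1.05 / 1.09 / 1.17 for equal volumes.

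A random intercept has power of about 0.85, 0.88 and 0.92 at ICC 0.10, 0.20 and 0.30 (d = 0.74). Its type I error is 0.04–0.06 when clinicians differ in level only.

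**Binary post-only outcome.** With 30% against 65% and the ICC on the latent scale, SE ratios are 0.98 / 0.99 / 1.01 / 1.03 / 1.05. Power is 0.80 / 0.80 / 0.81 / 0.82 / 0.82 unadjusted and 0.78 / 0.79 / 0.82 / 0.84 / 0.87 with Mantel-Haenszel. The size depends on the scenario and the ICC scale: at 30% in both arms, the separate simulation gave 1.04 / 1.04 / 1.11 / 1.15 at ICC 0.05 to 0.30.

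**Where the effect is absent or reverses.**
- Pre-post group-by-time contrast (change score, pre-post correlation 0.5 assumed): SE ratio 0.99–1.00 at every ICC, because a constant clinician effect cancels.
- CHEC effect varying between clinicians (ICC 0.10, effect SD 0.3 / 0.5): SE ratio without the term 0.98 / 0.93. Type I error is 0.050 / 0.069 without the term, 0.062 / 0.083 with fixed strata and 0.070 / 0.087 with a random intercept.

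**The case against.** The strongest objection is that Section 8 specifies a pre-post model with a group-by-time term, and in that model omitting clinician does no harm. This stands: the claim depends on discussion having no pre-intervention value. The single scheduled recording points that way, but a survey item could supply one, so the outcome's source has to be stated first.

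The second objection concerns the remedy. CHEC acts through the clinician's response, so clinicians may well differ in response as well as in level. A clinician intercept then makes the test somewhat anti-conservative, while the unadjusted test stays nearer 5%. This also stands as a cost. It is why arm differences should be shown by clinician and why a within-clinician analysis is useful as a check.

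Third, the gain is negligible at low ICC. For a binary outcome, which the wording of H5 suggests, the power change from Mantel-Haenszel in the 30% against 65% scenario is −2, −1 and +1 points at ICC 0, 0.05 and 0.10. That is correct and limits the severity.

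Finally, the open covariate list does not exclude clinician, and the impact aim is only preliminary. Both are true, but leaving room to add a term later is not prespecifying it, and the randomisation factor is the one covariate that the design itself identifies.

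**Conclusion.** The point holds, as a minor one. Clinician is a randomisation stratum and is absent from the stated between-arm model. In a post-only comparison the standard error is too large if clinicians differ in level: by about 1–2% at ICC 0.05, 4–5% at 0.10, 9–10% at 0.20 and 15–17% at 0.30 for a continuous outcome with equal volumes. For a binary outcome it ranges from nothing to about 15%, depending on ICC scale and event rates. The error is conservative.

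This rests on three assumptions: discussion is measured only at the recorded visit; clinicians differ in level, with ICCs that are assumed throughout; and the CHEC effect is roughly constant across clinicians. It does not apply to an outcome tested as a pre-post group-by-time contrast. H6 may be such an outcome.

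**What to change.** In Section 8:

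1. State how discussion of caregivers' needs is measured, on what scale, and whether a pre-intervention value exists.
2. If it is post-only, add clinician to the H5 analysis: a random intercept for a continuous or count-type score, or Mantel-Haenszel stratified by clinician if discussion is yes/no. Do the same for visit duration (H4), which has no stated model, if it is compared post-only.
3. Leave outcomes tested as a pre-post group-by-time contrast unchanged.
4. Describe the arm difference by clinician. As a sensitivity check, a t-test on within-clinician arm differences can be added. It uses only clinicians with dyads in both arms.

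**Cost.** The change is wording only, since Section 3.2 already lists provider among the abstracted chart items. If clinicians do not differ, at d = 0.74 a random intercept loses no power (0.81 against 0.81). Fixed strata lose about 1 point with equal volumes (0.81 to 0.80) and about 2 with the unequal volumes above (0.80 to 0.78). For a binary outcome at 30% against 65%, Mantel-Haenszel loses about 2 points (0.80 to 0.78). If the CHEC effect varies between clinicians, the added term raises type I error to about 0.06–0.09 in the cases simulated. The within-clinician t-test holds it at 0.052 / 0.048, but its power at ICC 0.10 and d = 0.74 is 0.75–0.78, against 0.83–0.86 for the random intercept across runs.

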3.2 Interviews, Focus Groups, Surveys, and/or Observations

A. Administration

▪ Timing and Frequency

- Caregiver baseline (pre-visit) surveys will take no more than 20 minutes and will be conducted prior to the visit; caregiver post-visit surveys will take no more than 25 minutes and will be conducted within one week of the visit, either in-clinic or remotely (via telephone and secure web survey or mail), based on the participant's preference. Separate post-visit, follow-up surveys will take no more than 15 minutes and will be conducted at 2 months and 6 months following the visit.
- Clinician baseline surveys will take no more than 5 minutes and will be conducted prior to the entire intervention period. Clinician post-intervention surveys and interviews will take no more than 30 total minutes and will be

conducted within 1 month of the conclusion of the intervention period. The post-intervention interviews will occur in-person or over the phone (based on the participant's preference) and will be audio-recorded.

- Medical chart abstraction will be conducted following enrollment/consent but prior to the visit. The medical visit will be audio-recorded.

▪ *Procedures For Audio And Visual Recording*

- Medical visits and interviews will be recorded (phone, video, or in-person encrypted recording) and stored on secure WCM servers via password protected tagged WCM computers.
- Audio-recordings will be transcribed by study co-investigators and will not leave the institution. The transcripts will also be stored on secure WCM servers via password protected tagged WCM computers.

▪ *Person Identifiers*

- Personal identifiers (e.g. names, email address, phone number, and address) will be collected for recruitment and compensation purposes. Voice and video recordings, as well as compensation identifiers, will be made on a voluntary basis.
- Patient data will be abstracted from the medical chart. Information obtained will include name, address, phone number, age, gender, race/ethnicity, provider, MRNs, electronic mail addresses and health diagnosis information including primary visit diagnosis code and clinic location (from defined time window), and health events (e.g. hospitalization, visit from home health aide). A partial HIPAA waiver will be requested for access to this information. All participants will be provided with a participant ID and their survey responses will be de-identified. Records will be maintained and kept in secure locations for a minimum of 3 years; the length of time specified according to WCM and HIPAA policies.

B. Study Instruments

The primary instruments for this study are validated, widely-used patient- and caregiver-reported outcomes (PCRO) assessments that are commonly used in health services research and clinical practice. These validated and reliable self-report measures include: Preparedness for Caregiving scale (Zwicker, 2010), CAPACITY measure (Van Houtven et al., 2019), Perceptions of Visit Communication (Talen et al., 2011), Caregiver Satisfaction with Primary Care Interactions (Clair et al., 2014; Haley et al., 1992), Perceived Self Efficacy in Primary Care Interactions (Maly et al., 1998), knowledge and use of resources (Thomas et al., 2017), caregiver anxiety and depressive symptoms (Mauer, 2012; Wild et al., 2014), and burden (Zarit, Reever & Bach-Peterson, 1980). We will use short forms when possible in order to reduce participant burden. We also developed several specific questions about caregivers' perception of the screening tool and knowledge of resources. All study instruments are attached to the IRB application in the WRG-HS system.

- Caregiver Subjects in CHEC (intervention group)

- CHEC Caregiver Screening Questions
- CHEC Caregiver Demographics
- CHEC Caregiver Pre-Test Questionnaire

- CHEC Visit Companion Checklist
- CHEC Caregiver 1-Week Post-Test Follow-Up Survey – Intervention
- CHEC Caregiver 2-Month Post-Test Follow-Up Survey – All Caregivers
- CHEC Caregiver 6-Month Post-Test Follow-Up Survey – All Caregivers
- Caregiver Subjects in control group
 - CHEC Caregiver Screening Questions
 - CHEC Caregiver Demographics
 - CHEC Caregiver Pre-Test Questionnaire
 - CHEC Caregiver 1-Week Post-Test Follow-Up Survey – Control
 - CHEC Caregiver 2-Month Post-Test Follow-Up Survey – All Caregivers
 - CHEC Caregiver 6-Month Post-Test Follow-Up Survey – All Caregivers
- Clinician Subjects
 - CHEC Clinician Pre-Test Demographics and Eligibility Questionnaire
 - CHEC Visit Companion Checklist + Provider Tip Sheet
 - CHEC Clinician Post-Test Questionnaire
 - CHEC Clinician Post-Test Interview Guide

4. Study Design

4.1 Study Population

The patient participant sample includes individuals who have upcoming appointments at the Center on Aging (COA) and are identified by COA clinicians as typically attending appointments by a family caregiver. Patient participants will vary in age, gender, race/ethnicity, and health conditions. The family caregiver sample will include caregivers of patients receiving care at the Center on Aging. They will also vary in age, gender, and race/ethnicity. Caregivers and patients will be recruited and enrolled as dyads. The clinician sample will include individuals who provide care at the Center on Aging. Clinicians will vary in age, be enrolled regardless of gender, and include those who have patient visits scheduled over the next year.

